10.2.3 Economic analysis

We expect skewness in the distribution of use of resources/costs ⁵². In the presence of skewness, the logarithmic transformation of data is not recommended, and the application of non-parametric tests can provide misleading results (economic studies aim to base the analysis on arithmetic means and not median values)^{53;54}. The non-parametric bootstrap test can be the most appropriate⁵⁴, since it does not require any assumptions about the normality of data and equality of the variance or shape of the distributions. The t-test can be safely used if the sample size is not too small⁵³. Depending on the level of skewness of data obtained we will make a judgement on which of these two methods can be safely applied. The mean costs estimates and (incremental) cost-effectiveness ratios, and conventional measures of variances will be reported⁴³.

10.2.4 Cohort analysis

The cohort of patients who decline to be randomised will be used to assess the external validity of the main study. Baseline characteristics of the cohort will be compared with those of the

study population using standard tests for the comparison of two independent samples (e.g. the t-test or Mann-Whitney test as appropriate). Outcome for the cohort will be compared with outcome for the two groups of study participants using the modelling approach described above.

11 Compliance and withdrawal

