3.2 Cohort study design

We anticipate that a large majority of participants who decline randomisation to the trial will opt for, and receive, surgery. Therefore, in order to assess the external validity of the trial results, we will recruit a cohort of children receiving surgery, randomly selected from those who decline to participate in the trial. Base-line characteristics will be collected for all who decline randomisation and a random sample of children receiving surgery will be followed up for 24 months. In addition a sample of older children and their carers from the Newcastle cohort will be invited to take part in an interview to measure their preferences and utilities.

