9.1 Data to be collected

All participants will be followed-up for 24 months from the date of initial randomisation. To minimise recall bias, data on sore throats will be gathered by a simple, structured daily health diary completed and returned by participants on a monthly basis for 24 months. Experience of similar studies suggests that with appropriate telephone reminders 90% of diaries will be returned completed.

In addition simple outcome questionnaires will be administered to trial and cohort study participants. Overall we anticipate an 80% response rate. Interview surveys will be done at 3, 12 and 24 months after randomisation. A baseline questionnaire will be completed by all participants upon recruitment to the trial. The greater frequency of data collection in the first 12 months is necessary in order to capture data on expected changes in direct and social costs to participants in the first 12 months. Experience also suggests that data on consultation rates and prescribed medication can be gathered most accurately and reliably from medical records. Manual abstraction will be performed by trained research nurses at the end of follow up for all participants

| Primary clinical outcome | Measurement method | When | Where |
|---|---|---|---|
| Number of events of recurrent sore throat | Self-completed diary (by parent or child) | Daily recording but collected four-weekly for 24 months | Participants' homes |
| Secondary clinical outcomes | Measurement method | When | Where |
| Number of events of recurrent sore throat, otitis media or URTI recorded by GPs | GP records | End of 24 month follow-up period | General practices (GP records) |
| Adverse events: re-referral for tonsillectomy; number of symptom-free days | Self-completed diary (by parent or child) and GP records | Daily recording but collected four-weekly for 24 months and end of 24 month follow-up period | Participants' homes (diary) and general practices (GP records) |

Table 1 Clinical outcome measures for trial and cohort studies

Table 2 Measuring treatment impact

| Impact | Measure | When | Where |
|---|--|-------------------------------------|--------------------|
| Costs to participants of the condition and its management | Questionnaire to children and parents | Base-line, 3, 12 and 24 months | Participant's home |
| Social costs: e.g. time off school and parental time off work | Self-completed diary (by parent or child) | Base-line, 3, 12 and 24 months | Participant's home |

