10.2 Statistical analysis

10.2.1 Main analysis

An intention to treat analysis will be performed. In particular, children randomised to nonsurgical conventional medical treatment will be retained in that group for the analysis even if they subsequently receive a tonsillectomy.

The primary clinical outcome measure will be the number of episodes of sore throat. This variable will be analysed using generalised linear modelling assuming a Poisson error structure with a log link function⁵¹. By fitting the difference between the two experimental groups as a fixed effect, interval estimates of the effect of tonsillectomy (in each of the first two years of follow up) will be generated. These estimates will then be used in the economic analysis.

The same approach will be used to analyse the other outcomes. A Poisson error structure will be assumed for data in the form or a count (such as the number of episodes of absence from school) and normal error structure adopted for continuous variables (such as the quality of life indices).

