10.2.2 Secondary analysis

The aim of secondary analysis is to determine whether we can identify groups of children who benefit from surgical treatment. It is hypothesised that disease severity may be an important factor. A severity index based on history of the condition during the year before entry to the study will be derived using data recorded in GP records. The relationship between severity and the effect of tonsillectomy will then be investigated using the modelling approach described above.

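### The cohort section judges representativeness by significance tests and sends the cohort outcome comparison to a model with no stated case-mix terms and no time origin that fits the cohort

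*Protocol*

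**What the plan says.** Protocol section 10.2.4 gives the cohort one purpose, the external validity of the trial, and sets two analyses.

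- **Baseline.** Cohort characteristics are compared with those of the trial population by "standard tests for the comparison of two independent samples", with the t-test and Mann-Whitney test as examples.
- **Outcome.** "Outcome for the cohort will be compared with outcome for the two groups of study participants using the modelling approach described above".

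The modelling approach is in section 10.2.1. For the primary outcome: "This variable will be analysed using generalised linear modelling assuming a Poisson error structure with a log link function". The one term described is group: "By fitting the difference between the two experimental groups as a fixed effect, interval estimates of the effect of tonsillectomy" are to be produced for each of the first two years. Section 10.2.2 uses the same cross-reference when it brings in a severity index from GP records: "The relationship between severity and the effect of tonsillectomy will then be investigated using the modelling approach described above".

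On who is in the cohort, section 3.2 states "Base-line characteristics will be collected for all who decline randomisation", but the children followed for 24 months are a random sample of decliners who receive surgery. Section 7 stratifies the cohort sampling by age. Section 10.1 sets the cohort at 142.

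On timing, section 9.1 states: "All participants will be followed-up for 24 months from the date of initial randomisation". Table 1 in that section covers both the trial and the cohort. Sections 6.1 and 11.1 tie the four-week limit for surgery to randomisation as well. Section 3.2 gives the length of cohort follow-up but not its start.

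**The concern.** The last objective in section 2.2 asks how well trial participants represent the target population. That is a question of how large the differences are. A p-value answers another question, and its answer depends on the number of children compared: a small cohort tends to look representative, and a large group of decliners tends not to, for the same true difference.

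The outcome comparison has a related weakness. A model with a group term alone is defensible between randomised arms because randomisation balances case mix on average. Cohort children declined randomisation and had surgery. Against the surgical arm, a group term mixes differences in severity, centre and age with any difference in response to surgery. Against the control arm, it mixes the surgery effect with self-selection and says little about external validity. Without a start date that applies to the cohort, the two sets of 24-month counts may also not cover comparable periods.

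Section 9.1.1 uses the cohort to validate the cost and benefit data and to judge how representative they are. A wrong reading would therefore carry into the economic conclusions.

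**Working it through.** **1. The plan's own figures reproduce.** Section 10.1 gives a difference of 1.5 days, SD 4.5, 80% power and 5% significance (two-sided assumed).

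- n per arm = 2 × (1.96 + 0.84)² × 4.5² / 1.5² = 142 after rounding up.
- Power at 142 against 142 is 80.2%, so a cohort of 142 does what section 10.1 says against one arm.
- 284 / 0.70 = 406, as in section 4.3.

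**2. Power of the baseline test for a true imbalance of 0.2 SD.** Power = Φ(0.2 / s − 1.96), with s = √(1/n₁ + 1/n₂). The imbalance detectable with 80% power is 2.80 × s. The half-width of a 95% interval for the standardised difference is about 1.96 × s.

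| Comparison | s | Power at 0.2 SD | Detectable at 80% | 95% half-width |
|---|---|---|---|---|
| 142 v 284 | 0.103 | 49% | 0.29 SD | 0.20 |
| 142 v 406 | 0.097 | 54% | 0.27 SD | 0.19 |
| 1,132 v 406 | 0.058 | 93% | 0.16 SD | 0.11 |

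The 1,132 is an assumption. Section 4.3 expects up to half of eligible children to decline and puts the other half at 566 a year, so 2 × 566 over two years of recruitment. The first two rows take 142 as the cohort number at baseline, since the protocol states no attrition allowance for it. If the trial's 30% were applied, 142 / 0.70 ≈ 203 against 406 gives s = 0.086 and power Φ(2.33 − 1.96) = 64%.

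The same true imbalance is thus found about half the time or nearly always, depending only on which children are counted as the cohort.

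**3. Case mix in a model with only a group term (illustration).** Assumptions: 142 per group, 3 episodes per child over two years in the surgical arm, no true difference in response, and case mix that multiplies the cohort rate by c. The Wald statistic is ln(c) / √[φ × (1/(142 × 3) + 1/(142 × 3c))], where φ is the dispersion. For c = 1.2 and φ = 1 it is 0.182 / 0.0656 = 2.78, so a difference is declared in 79% of studies.

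| c | φ = 1 | φ = 2 |
|---|---|---|
| 1.1 | 30% | 17% |
| 1.2 | 79% | 50% |
| 1.3 | 98% | 82% |

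**4. Undefined time origin (illustration).** Suppose that counting began at recruitment and that cohort children waited 3 months against 4 weeks in the trial arm. Take 1.5 episodes a year after surgery (midpoint of the 1 to 2 in the Appendix 2 scenario). Before surgery, take 4 a year (section 4.2.1) to 6.5 (midpoint of the 6 to 7 in the Appendix 2 scenario).

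- At 4 a year: trial 1.5 × (2 − 4/52) + 4 × 4/52 = 3.19; cohort 1.5 × 1.75 + 4 × 0.25 = 3.63. Excess 0.43, rate ratio 1.14.
- At 6.5 a year: trial 3.38; cohort 4.25. Excess 0.87, rate ratio 1.26.

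The 3-month wait is purely an assumption.

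**The case against.** The strongest reply is that the covariates are left open, not ruled out. A reader might infer that the protocol prescribes an unadjusted comparison. The text does not support that. Section 10.2.1 does not say that group is the only term, section 10.2.2 uses the same cross-reference for an analysis with a severity index, and section 7 stratifies cohort sampling by age. A covariate list is also commonly left to the SAP, which is not at hand. This stands, and limits the point: what can be said is that the described model has one term and was written for randomised arms. Section 10.2.2 uses severity to study how the surgery effect varies, not to remove confounding, and stratified sampling by age does not balance severity or centre.

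A reader might also infer that preoperative waiting is counted against the cohort. No section gives a cohort wait or says so; only the start date is undefined.

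One might quote 39% power for the 0.2 SD imbalance, which is the value for 142 against 142. Section 10.2.4 compares the cohort with the whole study population, so 49% to 54% applies. Likewise, each month of waiting at 4 to 6 episodes a year adds 0.33 to 0.50 episodes only gross. Net of 1.5 a year after surgery it is (4 − 1.5)/12 = 0.21 to (6 − 1.5)/12 = 0.38. Section 1.1 notes that reported histories often fail on close scrutiny, so the true rates before surgery may be lower still.

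Finally, section 10.2.4 nowhere treats the contrast with the control arm as a causal effect, and its description of the cohort could be read as all decliners. Both are fair. But section 3.2 restricts the followed cohort to children who receive surgery, so the two descriptions need to be reconciled.

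**Conclusion.** The point holds in a limited form. Section 10.2.4 fixes significance tests as the way to compare baseline characteristics, and these do not measure representativeness. At the stated cohort size, a 0.2 SD imbalance is missed about half the time (about a third if the cohort were enlarged for 30% attrition). The outcome comparison rests on a model whose only described term is group, applied to self-selected children, with no stated time origin that exists for them.

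The power figures rest on the protocol's sample sizes, a two-sided 5% test and the chosen 0.2 SD. The case-mix and waiting-time figures rest on assumed rates, waits and dispersion; they show what could happen, not what the plan implies will happen. No sample-size figure is wrong on this point, and the randomised comparison is untouched. What is at risk is the reading of external validity and the related use of the cohort in the economic evaluation.

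**What to change.** Amend section 10.2.4 as follows.

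1. Replace the baseline tests with standardised differences and 95% confidence intervals between trial participants and all decliners with baseline data. State which children form the cohort in each analysis, so that sections 3.2 and 10.2.4 agree.
2. Make cohort against randomised surgical arm the main outcome comparison, adjusted for age group, centre and the pre-entry severity index of section 10.2.2. Report the estimate and interval beside the unadjusted ones.
3. Label the contrast with the control arm descriptive.
4. Keep randomisation as the origin for trial children and define a comparable origin for the cohort, for example the date of recruitment. Count from operation only as a sensitivity analysis, where operation dates are recorded. As the main analysis it would leave unoperated children in the surgical arm without a start date and depart from intention to treat.

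The cost is slightly more analysis work. Section 3.2 already collects baseline data on decliners, and section 9.1 plans GP-record abstraction for all participants. The protocol does not say whether cohort operation dates are recorded, so the sensitivity analysis depends on that.

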6.1 Treatment

Tonsillectomy and adeno-tonsillectomy with adenoid curettage and tonsillectomy by dissection or bipolar diathermy. Most (80%) UK surgeons use the conventional dissection method⁶ and the remainder use bipolar diathermy. Both methods will be allowed in the trial according to surgical preference. Surgical intervention will take place within four weeks of randomisation.

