11.1 Subject compliance

Participants randomised to surgery will be followed up by research nurses to ensure compliance. Surgery will take place within 4 weeks of randomisation. Telephone reminders from research nurses will be used to encourage participants to return study diaries while both telephone from the trial manager and postal reminders will be used to encourage participants to return study questionnaires.

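### The cohort's outcomes come only from operated children, but they are compared with a surgical arm apparently analysed as randomised, so any shortfall in surgical uptake is mixed with representativeness

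*Protocol*

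**What the plan says.** Protocol section 3.2 defines the cohort by the operation: "we will recruit a cohort of children receiving surgery, randomly selected from those who decline to participate in the trial". Baseline data are gathered on everyone who declines, but outcome follow-up is narrower: "a random sample of children receiving surgery will be followed up for 24 months".

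Section 10.2.4 gives the purpose: "The cohort of patients who decline to be randomised will be used to assess the external validity of the main study". It then specifies the outcome analysis: "Outcome for the cohort will be compared with outcome for the two groups of study participants using the modelling approach described above". The same section also compares baseline characteristics of cohort and trial children.

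The approach referred to is that of section 10.2.1, which opens: "An intention to treat analysis will be performed". The one departure from allocation spelled out there is control to surgery: "children randomised to nonsurgical conventional medical treatment will be retained in that group for the analysis even if they subsequently receive a tonsillectomy". Children allocated to surgery but not operated on are covered only by the general sentence.

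The protocol intends high uptake in the surgical arm. Section 6.1 says: "Surgical intervention will take place within four weeks of randomisation". Section 11.1 adds: "Participants randomised to surgery will be followed up by research nurses to ensure compliance". It gives no expected rate of non-receipt, and it states no comparison restricted to trial children who had surgery.

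**The concern.** One side of the comparison is selected on having had the operation. The other, read as randomised, keeps every child allocated to it. A decliner who never reaches surgery cannot enter the followed-up cohort, while a child in the surgical arm who never reaches surgery stays in that arm.

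The comparison bears on a listed objective in section 2.2, how representative the trial children are. If uptake in the surgical arm is incomplete, the resulting gap could be read as the trial children being atypical, or it could hide a real difference in the other direction. Adjusting for case mix would not remove it, because it comes from how the two groups are defined. The primary randomised comparison is not touched.

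**Working it through.** **The plan's own figures first.** Section 10.1 gives 142 per arm, and the same number for the cohort, from a difference of 1.5 missed school days and an SD of 4.5, with 80% power at 5%. With n = 2(1.96 + 0.842)² × (4.5/1.5)² = 141.3, this rounds up to 142 and is reproduced (power at 142 is 80.2%). The stratum standard error, 2.0 × √(2/47) = 0.41, is reproduced too.

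**Inputs**
- SD of sore throats per year: 2.0 (section 10.1).
- Group sizes: 142 in the cohort and 142 in the surgical arm (section 10.1).
- Benefit of surgery: 1 to 2 episodes a year. Section 10.1 anticipates about 2 in the second year; the studies cited in section 1.3 run from about 0.5 to 1.75 a year.
- Share of the surgical arm not operated on, u: not in the protocol. Assumed values 0%, 5%, 10% and 20%.

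**Formula.** Suppose trial children are fully representative. Let S be the mean yearly count in operated children and U the mean in surgical-arm children who were not operated on.

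- Cohort mean = S
- Surgical-arm mean as randomised = (1 − u)S + uU
- Surgical arm minus cohort = u(U − S)

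If unoperated children fare like average controls, U − S is the benefit of surgery, and the built-in difference is u × benefit, with the cohort looking better.

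**Precision.** SE = 2.0 × √(2/142) = 0.237. The 95% interval half-width is 1.96 × 0.237 = 0.47 episodes a year, and the difference detectable with 80% power is 2.80 × 0.237 = 0.66.

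**Results.** Built-in difference in episodes a year, with the chance of a two-sided 5% rejection in brackets:

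| Not operated on (assumed) | Benefit 1.0 | Benefit 1.5 | Benefit 2.0 |
|---|---|---|---|
| 0% | 0 (5%) | 0 (5%) | 0 (5%) |
| 5% | 0.05 (5.5%) | 0.075 (6.2%) | 0.10 (7.1%) |
| 10% | 0.10 (7.1%) | 0.15 (9.7%) | 0.20 (13.4%) |
| 20% | 0.20 (13.4%) | 0.30 (24.4%) | 0.40 (39.2%) |

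These rejection rates use a normal approximation with equal SDs, not the planned Poisson model.

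**If the unoperated are children who got better.** U then lies below the control mean. With a benefit of 1 episode a year, unoperated children who have 1 episode fewer than average controls give U = S and no built-in difference. If they do better than that, U − S is negative and the direction reverses. The table therefore holds only under the assumption that unoperated children fare like average controls.

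**The case against.** The strongest reply is that the plan aims for complete uptake: surgery within four weeks, with nurses following up compliance. With u = 0 the difference is exactly zero. A reader might infer that the design builds in a difference even when trial children are fully representative. The protocol does not support that, because the difference depends on a non-receipt rate that it neither states nor implies. The crossover it does describe, from control to surgery, does not enter the contrast between cohort and surgical arm. This objection stands and makes the point conditional.

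Second, section 10.2.2 uses the same reference to the modelling approach, and there it plainly means the Poisson model with a log link. Section 10.2.4 might likewise borrow the model without the analysis set. That is possible, and reading the trial groups as randomised is an inference. It is still the natural one, since the section names the trial's two groups under an intention-to-treat plan and offers no other definition.

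Third, sections 4.3 and 10.2.4 describe the cohort more loosely, as children who declined randomisation. This does not undo section 3.2: only decliners receiving surgery are followed up, so only they can supply outcomes.

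Fourth, a reader might take 39% as the expected false-alarm rate. It needs both 20% non-receipt and a benefit of 2 episodes a year, and section 1.3 says no published trial has shown a benefit that large. At 5–10% non-receipt the difference is at most 0.20, well inside the interval half-width of 0.47. Section 10.2.4 also sets no significance rule for calling the trial unrepresentative.

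Last, this outcome contrast is not the only evidence on external validity. The baseline comparisons address it as well and do not depend on uptake.

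**Conclusion.** The point holds in conditional form. The followed-up cohort is defined by receipt of surgery, and on the natural reading the surgical arm is defined by allocation, so their difference mixes adherence with representativeness to the extent that surgical-arm children are not operated on.

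At an assumed 5–10% non-receipt the effect is small, 0.05 to 0.20 episodes a year. At 20% it is 0.20 to 0.40 and could be mistaken for unrepresentativeness. These sizes rest on an assumed uptake, a benefit of 1 to 2 episodes a year, unoperated children who fare like average controls, and a normal approximation. If the third assumption fails, neither size nor direction is assured. This concerns a secondary, non-randomised comparison, but one that serves a stated objective, so it should be tidied up.

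**What to change.** In section 10.2.4, add a comparison of the cohort with surgical-arm children who had the operation. Keep the intention-to-treat contrast beside it, and report uptake of surgery in the surgical arm with both. If uptake proves complete, the two contrasts coincide and nothing is lost. If it does not, the reader can separate adherence from representativeness, and the operated-only comparison will not look chosen after the event.

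The cost is a sentence or two and one extra model. Receipt of surgery should already be on record from the compliance follow-up in section 11.1. The downside is that the operated subset is not a randomised group, which matters little because the cohort comparison is not randomised either.
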